## **2.2 SUBJECTS**

### **2.2.1 Number of Subjects**

A total of 30 subjects will be treated on the study at 3 investigational sites in US.

### **2.2.2 Diagnosis and Main Criteria for Inclusion**

Subjects will be SK treatment naïve males and females between age of 30 and 75 years old with stable clinically typical SK. For each subject, 3 eligible target SKs; 2 target SKs must be on the face, and the additional 1 target SK must be on the neck or décolletage. Up to 4 additional non-target SKs may be identified on the face, neck or décolletage.

### **2.2.3 Study Population Characteristics**

Subjects with a clinical diagnosis of SK who meet all the inclusion criteria and none of the exclusion criteria will be eligible to enroll in the study. Detailed inclusion and exclusion criteria, see protocol sections 7.1 and 7.2.

### **2.2.4 Replacement Subjects**

If a subject is enrolled to the study but does not receive a dose of study drug, then the subject may be replaced. Subjects that are determined to be screen failures may be rescreened for the study and if determined to be eligible for the study they may be enrolled under using the same subject identifier and must sign a new informed consent form.

## **2.3 TREATMENT AND RANDOMIZATION**

### **2.3.1 Study Medications, Treatment, and Mode of Administration**

A-101 Solution, 40% (w/w), external topical.

### **2.3.2 Randomization**

Not applicable.

### **2.3.3 Administration of Treatment**

At Visits 2, 5, and 7, each target and non-target SK must be treated by a study trained healthcare provider at the site.

At Visits 5 and 7, all identified target and non-target SKs that have a PLA grade of  $\geq 1$  will be retreated with the solution. If in the investigator's opinion, the lesion is not appropriate for re-treatment, treatment will be withheld.

### **2.3.4 Duration of Treatment**

The duration of the study participation is anticipated to be a maximum of 134 days per subject. The final visit (Visit 11), has a maximum allowable visit window of 7 days.

## **2.4 ASSESSMENTS**

### **2.4.1 Evaluators**

The investigator, a designated and appropriately trained staff member (e.g., sub investigator) or the subject will perform the study assessments according to the defined schedules.

Similar lighting conditions and subject positioning should be used for all evaluations for a given subject.

### **2.4.2 Evaluations – Efficacy**

#### **2.4.2.1 Physician's Lesion Assessment (PLA)**

The PLA is the investigator's assessment of the severity of the target and non-target SK at a particular time point. The investigator may refer to other evaluations (e.g., prior photographs) to assist with these assessments.

At Visits 1, 2, 3, 4, 5, 7, 10, and 11 the investigator will assess the target and non-target SK using the scale below and report the one integer that best describes the severity of the target or non-target SK. At Visit 2 and if applicable at Visit 5 and Visit 7, the investigator must complete the PLA prior to the study medication treatment. The description of PLA grade is as shown in the table below.

Grade	Descriptor
0	Clear: no visible seborrheic keratosis lesion
1	Near Clear: a visible seborrheic keratosis lesion with a surface appearance different from the surrounding skin (not elevated)
2	Thin: a visible seborrheic keratosis lesion (thickness $\leq$ 1mm)
3	Thick: a visible seborrheic keratosis lesion (thickness $>$ 1mm)

In order for a subject to be eligible for screening and enrollment to the study, each target and non-target SK must have a PLA grade of  $\geq 2$ .

#### **2.4.2.2 SK Dimensions**

At Visit 1 and Visit 2 prior to study enrollment, the investigator will measure the diameter and thickness of each target and non-target SK using the ruler provided.

The investigator must measure the diameter of the longest axis of each target and non-target SK in millimeters (mm) as follows:

- Diameter (i.e., the length of the longest axis)
- Thickness (height above the surrounding skin)

The PLA (the thickness) of the target and non-target SKs will be measured by the investigator at Visits 3, 4, 5, 7, 10, and 11. When the visit coincides with treatment (Visits 2, 5 and 7), the thickness must be measured prior to the application of study medication.

#### **2.4.2.3 Subject Satisfaction Assessment**

Subjects will be asked to assess their level of satisfaction regarding the study medication treatment experience. The subject survey will be completed at Visits 2, 3, 6 (only if treated at Visit 5), 8 (only if treated at Visit 7), 10, and 11.

The subject satisfaction assessments contain single and multiple choice questions. Three sets of questionnaires are designed for assessments at Day 1/Visit 2 prior to treatment, assessments for treatment experience after each treatment, and assessments at the end of study.

### **2.4.3 Evaluations – Safety**

#### **2.4.3.1 Adverse Events**

Non-serious AEs will be recorded starting with the subject's first study medication treatment at Visit 2 and continuing through Visit 11. All SAEs regardless of relationship to study medication will be collected and reported from the time the Informed Consent is signed through Visit 11.

#### **2.4.3.2 Vital Signs**

Vital signs will be measured by a qualified staff member at Visit 1, Visit 2, Visit 5, Visit 7, Visit 10, and Visit 11. The following items will be measured:

- Body temperature
- Pulse rate

- Respiration rate
- Blood pressure (systolic and diastolic) after the subject sits quietly for at least 5 minutes
- Height (at Visit 1 only)
- Weight (at Visit 1 only)

Any measure that is, in the opinion of the investigator, abnormal AND clinically significant (CS) must be recorded as history if found prior to the first study medication treatment or as an AE if found after the first study medication treatment begins.

A systolic blood pressure >140mm Hg or a diastolic blood pressure >90mm Hg is considered abnormal and therefore must be defined as CS or non-clinically significant (NCS) on the Case Report Forms (CRFs).

#### **2.4.4 Other Evaluations**

At Visit 1, the investigator or designee will collect demographic information including date of birth, sex at birth, race, ethnicity, and Fitzpatrick Skin Type for each subject.

Skin Type Classification	Description
Type I	Always burns, never tans (pale white; blond or red hair; blue eyes; freckles)
Type II	Usually burns, tans minimally (white; fair; blond or red hair; blue, green, or hazel eyes)
Type III	Sometimes mild burn, tans uniformly (cream white; fair with any hair or eye color)
Type IV	Burns minimally, always tans well (moderate brown)
Type V	Very rarely burns, tans very easily (dark brown)
Type VI	Never burns, never tans (deeply pigmented dark brown to darkest brown)

### **3 STATISTICAL METHODOLOGY**

---

This plan describes methods planned for the analysis and display of efficacy (PLA-based analyses only) and safety endpoints. Summaries will be based on mainly descriptive summaries for each assessment. A separate analysis plan will detail the analysis methods used for analyzing subject satisfaction assessments and its relationship with PLA.

#### **3.1 GENERAL STATISTICAL CONSIDERATIONS**

Descriptive statistics (mean, standard deviation [Std Dev], median, minimum [Min], and maximum [Max]) will be used for continuous variables; number and percentage of subjects will be used for discrete variables. In general, the last measurement prior to the first dose of study treatment will be used as the baseline value. Nominal visits will be used for by-visit summaries.

All tabulations of summary statistics, graphical presentations, and statistical analyses will be performed using SAS® Version 9.2 or higher.

#### **3.2 ANALYSIS POPULATION AND DISPOSITION OF SUBJECTS**

##### **3.2.1 Data Sets Analyzed**

Intent-to-Treat (ITT) analysis set includes all enrolled subjects. This is the analysis set for all analyses. A subject is considered enrolled if at least one study treatment is applied.

##### **3.2.2 Disposition of Subjects**

The numbers of subjects screened (ie, signed informed consent), enrolled, discontinued from treatment (by reason), and replaced will be presented.

#### **3.3 DEMOGRAPHIC AND OTHER BASELINE CHARACTERISTICS**

Demographic and baseline characteristics will be summarized. Gender, race, ethnicity, and Fitzpatrick skin type will be summarized with number and percentage presented for each category. Age, height, weight will be described with summary statistics (n, mean, Std Dev, median, minimum, and maximum).

#### **3.4 MEDICAL HISTORY**

Medical history will be summarized by body system class.

### **3.5 PRIOR/CONCOMITANT MEDICATIONS**

The number and percentage of prior medications, and concomitant medications will be summarized by Anatomical Therapeutic Chemical (ATC) and preferred term (PT) separately.

Medications taken any time prior to the first study treatment are counted as prior medications. Those taken any time on or after the first application of study medication through 30 days after the last application of study are counted as concomitant.

Subject will be counted only once within each classification. The same subject may contribute to two or more preferred terms within the same ATC classification.

### **3.6 STUDY DRUG EXPOSURE AND COMPLIANCE**

Duration of treatment (Last study treatment application date – First study treatment application date + 1) will be summarized descriptively. Number and percentage of subjects at each visit will be summarized by the number of target/non-target lesions being treated. In addition, number and percentage of subjects with re-treatment will be summarized for the applicable visits.

### **3.7 EFFICACY ANALYSIS – PLA ANALYSES**

PLA related parameters will be summarized at lesion level and at subject level.

At each visit or applicable visit, the following analyses will be performed:

- Number and percentage of lesions by PLA score categories (clear, near-clear, thin, and thick), overall and by target/non-target lesions; separately for face target lesions, and for neck target lesions;
- Summary statistics on PLA score (mean of all lesions, mean of target lesions, and non-target lesions, respectively);
- Summary statistics on percentage of lesions that are clear (PLA=0); separately for face target lesions, and for neck target lesions;
- Summary statistics on percentage of lesions that are clear or near clear (PLA=0 or 1); separately for face target lesions, and for neck target lesions;
- Number and percentage of lesions by location (face, neck, or décolletage), overall and by target/non-target lesions;

### **3.8 SAFETY ANALYSIS**

The safety and tolerability of the investigational products will be determined by reported AEs, and vital signs.

#### **3.8.1 Adverse Events**

All subjects will be assessed regularly for the potential occurrence of adverse events (AEs) from the date of informed consent to 30 days after the last study treatment. The incidence of treatment-emergent AEs (TEAEs) will be summarized and tabulated using MedDRA (version 22.0), by System Organ Class (SOC) and Preferred Term (PT).

An overview of adverse events for the ITT analysis set will be provided, summarizing the incidence of the following:

- Count of TEAEs;
- Subjects with TEAEs;
- Count of Treatment-emergent serious AEs (TESAE);
- Subjects with TESAE;
- TEAE by maximum severity;
- TESAE by maximum severity;
- Subjects with TEAEs that lead to discontinuation of study;
- Subjects with TESAEs that lead to discontinuation of study;
- Subjects with Related TEAEs;
- Subjects with Related TESAEs.

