Descriptive statistics will be used to summarize the data. Descriptive statistics will be used to summarize the effectiveness for this study. The focus of the analyses will be the evaluation of the relationship between lesion outcomes and subject satisfaction scores from each of the subject satisfaction scales. Because satisfaction is assessed on a subject level and not for each individual lesion, it will be necessary to first summarize multiple lesion outcomes into one score for each subject visit. The analyses will then be implemented at each applicable visit by calculating separate Pearson correlations coefficients between (1) mean change from baseline in per-subject averaged PLA scores across all lesions, and (2) each subject satisfaction scale score at the visit. As a sensitivity analysis, the above statistics will also be calculated using Spearman's rank-order correlation. Exploratory analyses similar to the above will also be conducted between (1) per-subject averaged percent of treated lesions clear (PLA = 0) and (2) each subject satisfaction scale score. A similar exploratory analysis will also be conducted using per-subject averaged percent of lesions clear or near-clear (PLA < 2). Additional multiple regression models may be used across groups of subject satisfaction scales, depending on the pattern of individual subject satisfaction scale outcomes.

Safety Analysis:

Safety endpoints for adverse events (AEs) include the following: incidences of all treatment-emergent AEs (TEAEs), and all serious AEs (SAEs); by severity, and discontinuation of subjects from study due to AEs. Safety endpoints for AEs will be specified in the statistical analysis plan (SAP). All safety endpoints will be summarized using descriptive statistics.

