¹²A-101 40% will be applied to each target and non-target SK by a study trained healthcare provider at the site. Each target and non-target SK will be treated with A-101 40% following confirmation of subject eligibility and study enrollment at Visit 2. If a target or non-target SK meets the criteria for retreatment as defined in Section 9.5, the SK will be retreated at Visit 5 and Visit 7. Following application of A-101 40%, subjects must NOT wash/submerge a target and non-target SK for at least 6 hours and they must NOT apply any topical products to any target or non-target SK for at least 6 hours.

¹³Subjects will be asked to assess how satisfied they are with the treatment experience they received for the target and non-target SKs at the specified visits. On Visit 2 the subject will complete the assessment prior to application of A-101 40%. On Visit 3 the subjects will complete the assessment approximately 24 hours after the treatment. On Visit 6 and Visit 8 the subjects will complete the assessment approximately 1 week after the treatment, only if the subject received treatment on Visit 5 or Visit 7. The subject will complete the assessment during the Visit 10 and Visit 11.

¹⁴All concomitant therapies including (topical and oral) prescription medications, over the counter medications, natural supplements and non-drug therapies including chiropractic, physical therapy, and energy-based therapy must be documented in the subject CRF. Subjects must not apply any topical products (*e.g.*, moisturizers, sunscreen, etc.) to their target and non-target SKs within 12 hours prior to any study visit.

¹⁵The reporting period for SAEs begins when the subject signs the informed consent form. Refer to Section 11.6 for instructions on the reporting of SAEs. Non-serious clinical adverse events will be collected following the application of the study medication at Visit 2 and continue through Visit 11. All safety reporting (AEs and SAEs) will conclude at Visit 11.

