8.3. Concomitant Medications

Concomitant therapies are any new or existing therapy received from Visit 1 until discharge from the study.

Concomitant therapies include drug (*e.g.*, prescription, over-the-counter [OTC]) and non-drug (*e.g.*, chiropractic, physical therapy, energy-based treatments) therapies. Subjects will refrain from receipt of any therapy in compliance with the inclusion/exclusion criteria.

All new or modified concomitant therapies used during the study must be recorded in the subject CRF.

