11.6. Reporting Adverse Events

At each post enrollment visit, the investigator or designee will question the subject to elicit AEs using a non-directive question such as “Has there been any change in your health since the previous study visit?”

The investigator or designee will monitor the subject for at least 20 minutes after the Treatment Completion Time at Visit 2, and if applicable at Visit 5 and Visit 7 to elicit AEs in a similar manner.

If appropriate, based on the subject’s response to non-directed questioning regarding AEs, the investigator or designee will follow-up with directed questions and appropriate evaluations.

Non-serious AEs should be recorded starting with the subject’s first study medication treatment at Visit 2 and continuing through Visit 11.

All SAEs regardless of relationship to study medication must be collected and reported to Aclaris Therapeutics, Inc. from the time the Informed Consent is signed through Visit 11.

Upon becoming aware of a SAE the investigator must:

1. Take the appropriate medical action to ensure the subject’s safety
2. Immediately inform the Safety Monitor of the SAE:

[name]
Aclaris Therapeutics, Inc.
[name]
[name]
[contact]
Serious Adverse Event [contact]
Email: [contact]

3. Within 24-hours of becoming aware of the event, a SAE report form, an AE CRF and any other relevant information (*e.g.*, concomitant medication CRF, medical history CRF, laboratory test results) must be faxed to the SAE Fax line listed above.
4. Monitor and document the progress of the SAE until it resolves or, if not resolved after the subject’s last study visit, until in the opinion of the investigator the SAE reaches a clinically stable outcome with or without sequelae AND the investigator and Safety Monitor agree that the SAE is satisfactorily resolved.
5. Inform the Safety Monitor of SAE updates by telephone followed by an SAE form update sent by fax or by e mail.

6. Comply with the appropriate regulatory requirements and Aclaris Therapeutics, Inc. instructions regarding reporting of the SAE to the responsible Institutional Review Board (IRB) or Ethics Committee (EC).

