#### **1.1.3 Safety Assessments**

Safety assessments include adverse events, change in vital signs, and concomitant medication use.

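### The SAP's 30-day post-treatment windows for adverse events and concomitant medications end well before Visit 11, and a treatment-emergent event is never defined

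*SAP*

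**What the plan says.** **Adverse events.** SAP 3.8.1 has all subjects assessed for AEs "from the date of informed consent to 30 days after the last study treatment" and goes straight on to the TEAE tabulation. No other window appears in that section.

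The collection rules differ. SAP 2.4.3.1 records non-serious AEs from the "first study medication treatment at Visit 2 and continuing through Visit 11". Protocol 11.6 says the same for non-serious AEs, and that SAEs "must be collected and reported to Aclaris Therapeutics, Inc. from the time the Informed Consent is signed through Visit 11". Footnote 15 to the schedule (Protocol Table 3, repeated in SAP 2.1) adds: "All safety reporting (AEs and SAEs) will conclude at Visit 11".

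The protocol synopsis lists the incidence of all SAEs, as well as of TEAEs, among the safety endpoints and leaves their specification to the SAP. SAP 3.8.1 lists only treatment-emergent counts (TEAE and TESAE). Neither document says what makes an event treatment-emergent.

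**Medications.** SAP 3.5 calls anything taken before the first treatment prior. Medications taken from the first application "through 30 days after the last application of study are counted as concomitant". Protocol 8.3 states: "Concomitant therapies are any new or existing therapy received from Visit 1 until discharge from the study". SAP 1.1.3 treats this as safety information: "Safety assessments include adverse events, change in vital signs, and concomitant medication use". The SAP 3.5 table is organised by ATC class, while footnote 14 to the schedule also requires non-drug therapies to be recorded.

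**The concern.** The data are collected to Visit 11, but the analysis text stops earlier. The two halves differ in strength.

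For medications, SAP 3.5 is a counting rule. A drug first taken more than 30 days after the last application is neither prior nor concomitant, so it drops out.

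For AEs, the 30-day sentence speaks of assessment and not of tabulation. One programmer could take it as the TEAE window because nothing else in the section supplies one; another could follow SAP 2.4.3.1. The same database would then give two different sets of tables. Under the first reading, AEs and SAEs with onset or worsening after the cut-off would be missing.

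Two features of this study make late events worth keeping:

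- Vital signs are measured at Visits 10 and 11, and a clinically significant abnormality after first treatment must be recorded as an AE (Protocol 11.1). The value would appear in the SAP 3.8.2 summaries while a new AE arising from it could be absent from the AE tables.
- The schedule has no separate assessment of local skin reactions, so a late skin effect is captured only as an AE.

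**Working it through.** **Timeline check.** Screening Day -13 to 0 is 14 days, Day 1 to 113 is 113 days, and the Visit 11 window adds 7: 14 + 113 + 7 = 134. This reproduces the maximum participation stated in SAP 2.3.4.

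**Inputs.** Treatment visits are Visit 2 (Day 1), Visit 5 (Day 15 ± 1) and Visit 7 (Day 29 ± 1). Follow-up visits are Visit 8 (Day 36 ± 1), Visit 9 (Day 57 ± 7), Visit 10 (Day 85 ± 7) and Visit 11 (Day 113 ± 7). AEs and concomitant therapies are scheduled at all of them. The last treatment can be at Visit 2, 5 or 7, because lesions are retreated only at PLA ≥ 1 and a subject may refuse retreatment and stay in the study (Protocol 6.4).

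**Formulas.** Cut-off = last treatment day + 30. Days outside = Visit 11 day − cut-off. Share = days outside / Visit 11 day.

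| Last treatment | Nominal cut-off | Days outside (Visit 11 on Day 113) | Share | Scheduled visits after cut-off |
|---|---|---|---|---|
| Visit 2 | 1 + 30 = Day 31 | 113 − 31 = 82 | 72.6% | 8, 9, 10, 11 |
| Visit 5 | 15 + 30 = Day 45 | 113 − 45 = 68 | 60.2% | 9, 10, 11 |
| Visit 7 | 29 + 30 = Day 59 | 113 − 59 = 54 | 47.8% | 10, 11 |

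**With visit windows** (Visit 11 on Day 106 to 120):

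- Last treated at Visit 2: 106 − 31 = 75 to 120 − 31 = 89 days (70.8% to 74.2%).
- Last treated at Visit 5, cut-off Day 44 to 46: 106 − 46 = 60 to 120 − 44 = 76 days (56.6% to 63.3%).
- Last treated at Visit 7, cut-off Day 58 to 60: 106 − 60 = 46 to 120 − 58 = 62 days (43.4% to 51.7%).

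The latest possible cut-off is Day 60 and the earliest possible Visit 10 is 85 − 7 = Day 78, which is 18 days later. The dates of Visits 10 and 11 are therefore always outside. Visit 9 (Day 50 to 64) can fall on either side when the last treatment is at Visit 7.

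**Start points.** The consent start in SAP 3.8.1 is correct for SAEs. It conflicts with SAP 2.4.3.1 for non-serious AEs, which are recorded only from the first application. SAEs between consent and first application are collected but have no planned summary. SAP 3.5 starts concomitant use at the first application and Protocol 8.3 at Visit 1; no drug is lost by this, since earlier use counts as prior.

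**The case against.** The best reply is that the AE sentence is stray wording. It describes assessment, and it starts at consent, so it cannot be a treatment-emergent window as written. SAP 3.8 opens by basing safety on reported AEs, reporting runs to Visit 11, and Protocol 12 asks for AE summaries with no 30-day limit. This is a fair reading, and it is why the loss of AEs is only possible. It does not supply a TEAE definition or remove the conflicting sentence, and it does nothing for SAP 3.5, where the exclusion is explicit.

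A second reply is that days are not events. That stands. The TEAE rates on A-101 quoted in Protocol section 4 (24.2%, 18.9% and 17.0% of subjects) give 7.3, 5.7 and 5.1 of 30 subjects with any TEAE. If each had one event, with onset uniform over 113 days, 47.8% of these, or 2.4 to 3.5 subjects, would have onset after Day 59. Those studies differ in follow-up and number of applications, so this shows an order of magnitude only. In addition, an event reported at Visit 10 may have begun before the cut-off, and events or medications that started earlier still count.

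A third reply is that non-drug therapies are a separate matter. That also stands. Several lesion treatments prohibited in Protocol 8.4 (laser or other energy-based therapy, liquid nitrogen, electrodesiccation, curettage) are procedures that an ATC table would not show whatever its end date. The main point does not depend on this.

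**Conclusion.** The concern holds. Both 30-day windows contradict the collection periods, and for AEs the contradiction lies within the SAP itself. Under SAP 3.5 as written, medications first taken after the cut-off would be left out. Late AEs and SAEs may be left out, depending on how the undefined TEAE is programmed.

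At nominal visits, 54 to 82 of 113 days lie outside. The typical figure is about 54 days (48%), assuming that most subjects still have a lesion with PLA ≥ 1 at Visit 7 and are treated there. The earlier studies make this plausible: all four target lesions were clear at the end in only 4.0%, 7.8% and 10.9% of subjects on A-101. The number of events affected cannot be reliably estimated from the documents.

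This is a tabulation defect in a single-arm study with descriptive safety tables. Collection and the PLA and satisfaction endpoints are untouched. It should be fixed, but it does not threaten the study's main result.

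**What to change.** **SAP 3.8.1.** Replace the 30-day window. Define a TEAE as an AE with onset or worsening from the first application through Visit 11 or withdrawal, and use that definition for the TEAE and TESAE tables. Summarise all SAEs from consent through Visit 11. Because SAP 3.2.1 limits the analysis set to treated subjects, list separately any SAE in a consented subject who was never treated.

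**SAP 3.5.** Count medications as concomitant from the first application through Visit 11 or discharge, and note that the start differs from Protocol 8.3 because earlier use is tabulated as prior.

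**Optional.** List non-drug therapies on treated lesions over the same period. A 30-day summary can be kept as supplementary if it is wanted.

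**Cost.** Two or three sentences and a listing or two in the SAP, with no new data collection. AE and medication counts may rise slightly.
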